### ***3.1.1.2. Definition of Dose-limiting Toxicity***

DLTs are defined as AEs (graded according to CTCAE version 5) occurring within 5 weeks after first IMP administration in Cycle 1 of Part 1 and that are considered possibly or probably related to IMP and meet any of the following criteria:

- Grade 4 myelosuppression (i.e., anemia, thrombocytopenia, or neutropenia) lasting more than 1 week, or more than 3 weeks following intervention (e.g., blood transfusion or granulocyte-macrophage colony-stimulating factor [GM-CSF])
- Any other Grade 4 hematological AE
- Grade  $\geq 3$  thrombocytopenia associated with bleeding
- Grade  $\geq 3$  febrile neutropenia (i.e., fever concurrent with neutropenia) lasting more than 5 days despite use of growth factors and antibiotics
- Grade 4 infusion-related reactions/anaphylaxis
- Grade 3 infusion-related reactions (excluding fever and Grade 3 abnormal laboratory values) that do not resolve to Grade  $\leq 1$  within 5 days of onset.
- Any non-hematological Grade  $\geq 3$  AE that is not listed in the list of exemptions below

DLTs must be entered onto the clinical AE report form and be reported from site to sponsor within 24 hours of the investigator's first knowledge of the event (see [Section 7.4.5.2](#)). If any of the side effects mentioned in the DLT definitions occur during Cycle 2 in Part 1, these will be discussed at the first upcoming preplanned DMC meeting, and the Sponsor Safety Committee will evaluate the DMC recommendations for further dosing.

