### 2.2. Endpoints

#### 2.2.1. Primary Endpoints

The primary endpoint of Part 1 is number of DLTs.

The primary endpoint of Part 2 is number and severity of TEAEs.

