### ***3.1.1.1. Dose Escalation and Stopping Rules***

As detailed in [Section 4.4](#), a DMC will be formed to independently review the safety data from previous dose level(s) and make recommendations on whether dose escalation should continue. Based on the DMC recommendation, following review by the sponsor, the doses may be escalated or reduced and may be lower than the starting dose.

The starting treatment dose of lutetium-177 in Part 1 will be 10 mCi. Planned dose escalations (with a 3+3 design) are 25, 50, 65, and 85 mCi. Up to 1 additional dose level may be recruited to investigate an intermediate dose of investigational medicinal product (IMP), if warranted based on the safety findings from previous dose level(s). The requirement for an additional dose level will be agreed with the sponsor in consultation with the DMC and will be documented in the

Trial Master File. Dosing at any additional dose level will be subject to the same dose-escalation rules as for the planned dose levels, as described below. The maximum planned dose is 85 mCi.

Initially, 1 patient will be allocated to Dose Level 1 and subsequent dose escalations will be conducted using a classic 3+3 design. If no treatment-related Grade 3 or higher AEs are observed in the first patient, escalation from Dose Level 1 to Dose Level 2 will proceed with 3 patients being allocated to Dose Level 2, after DMC evaluation and recommendation. If a Grade 3 or higher treatment-related AE occurs, a further 2 patients will be enrolled at Dose Level 1.

The DMC will receive all SAE on an ongoing basis. The DMC will make the final assessment of whether the event qualifies as a DLT.

The first enrolled patient in each dose level will be observed for a minimum of two weeks after the treatment dose before subsequent patients will be dosed at the same dose. During the two weeks of observation, safety surveillance will focus on DLTs (including myelosuppression). If a DLT is observed in the first patient, a second patient will be included and observed for a minimum of two weeks after the treatment dose before the third patient is included. If no DLT is observed in the first patient, two subsequent patients will receive the treatment dose, but at least two days apart.

Escalation and de-escalation decisions will then be determined by the number of DLTs (as defined in [Section 3.1.1.2](#)) observed during Cycle 1 and the number of patients evaluable for DLTs, as follows.

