#### **4.4. *Data Monitoring Committee***

An external DMC will be established to assure patient safety and will function independently of all other individuals associated with the conduct of the trial, including site investigators participating in the trial. The DMC will consist of a minimum of 2 physicians whose expertise covers relevant specialties.

During the conduct of Part 1, following completion of the first 5-week treatment cycle (Cycle 1) for the last patient in each dose level, the DMC will evaluate available safety information and recommend trial continuation or termination. If continuation is recommended, the DMC will recommend to the sponsor whether the dose should be escalated, de-escalated, or held at the same level. In the absence of DLT during the first two weeks of the first patient enrolled in each dose level, the enrollment to the dose level will continue without the need of feedback from the DMC.

If any of the side effects mentioned in the DLT definitions ([Section 3.1.1.2](#)) occurs during Cycle 2 in Part 1, these will be discussed at the first upcoming preplanned DMC meeting, and the internal Sponsor Safety Committee will evaluate the external DMC recommendations for further dosing. During Part 1 and until the DMC meeting in Part 2, the sponsor will share with the DMC all SAEs occurring during the trial and an unplanned DMC meeting can be held at the request of either the DMC or the Sponsor Safety Committee.

The DMC will evaluate the totality of cumulated absorbed dose calculated based on the dosimetry data from Part 1, and all available DLTs and other non-DLT toxicities from cycles 1 and 2 in all patients dosed in Part 1, to guide whether the maximum of five cycles is feasible in Part 2.

During the conduct of Part 2, an additional DMC meeting will be held when the eighth patient has completed dosing in Cycle 1 to evaluate whether the trial should be modified, stopped, or continue unchanged. The Sponsor Safety Committee will evaluate the recommendations from the DMC after each DMC meeting. Any significant finding/recommendation from the DMC and endorsed by the Sponsor Safety Committee will be communicated to the regulatory authorities and Institutional Review Board (IRB)/Ethics Committee (EC) as appropriate, and to the sites.

Responsibilities, procedures, content of the DMC packages, and workflow of the DMC are specified in the DMC Charter.

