## **5.3. Method of Treatment Assignment**

This is an open-label trial and is not subject to randomization. After dose level 1 in Part 1, patients will be allocated to the highest dose level cleared by the DMC.

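### The dose-limiting toxicity (DLT) definition names no related death and sets its two general haematological criteria at Grade 4, so on a literal reading a narrow group of related fatal marrow events meets no criterion (minor)

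*Combined protocol and SAP*

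**What the plan says.** Section 3.1.1.2 defines a DLT as a CTCAE version 5 graded adverse event that occurs within 5 weeks of the first administration in Cycle 1 of Part 1, is possibly or probably related to the product, and meets at least one of seven criteria. Two of these are general haematological criteria:

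- "Grade 4 myelosuppression (i.e., anemia, thrombocytopenia, or neutropenia) lasting more than 1 week, or more than 3 weeks following intervention" (the text gives transfusion and GM-CSF as examples of intervention)
- "Any other Grade 4 hematological AE"

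Section 2.2.1 states: "The primary endpoint of Part 1 is number of DLTs". Section 3.1.1.1 states: "Escalation and de-escalation decisions will then be determined by the number of DLTs", and refers back to Section 3.1.1.2 for what a DLT is. On adjudication, Section 3.1.1.1 gives the DMC all serious adverse events as they occur and adds: "The DMC will make the final assessment of whether the event qualifies as a DLT".

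**The concern.** Elsewhere the plan uses open-ended grades where it wants them. Three of the seven criteria say Grade 3 or above, and the Dose Level 1 rule in Section 3.1.1.1 refers to Grade 3 or higher. The two general haematological criteria do neither, and nothing in the document says that Grade 4 there means Grade 4 or worse, or that a related death is always a DLT. Taken at its word, the list can count a survivor with prolonged Grade 4 cytopenia and fail to count a patient who died of the same toxicity sooner.

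Marrow toxicity is the plan's own leading radiation concern. Sections 1.2.2.2 and 1.2.3 report mouse deaths from non-recovering myelosuppression, at doses above the estimated marrow limit. Section 1.2.1 reports cytopenia-related events in 81.7% and 87.5% of patients in the two trials of the iodine-131 product. In a first-in-human paediatric trial, the rule that drives escalation should count a related marrow death without any need for interpretation.

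**Working it through.** The plan states no figure on this point. The check is a reading of the criteria against the kinds of related death that could occur.

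**Step 1: the grades used in Section 3.1.1.2.**
- Grade 3 or above (three criteria): thrombocytopenia with bleeding; febrile neutropenia lasting more than 5 days despite treatment; non-haematological events outside the exemption list.
- Grade 4 (three criteria): myelosuppression with a duration condition; the haematological catch-all; infusion reaction or anaphylaxis.
- Grade 3 (one criterion): infusion reaction not resolving within 5 days.
- Total: 3 + 3 + 1 = 7. None names death or Grade 5.

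**Step 2: related deaths set against the list.**
- Death coded as a non-haematological event, such as sepsis, haemorrhage or anaphylaxis: covered by the non-haematological criterion. The exemptions are limited to Grade 3 events.
- Fatal thrombocytopenia with bleeding: covered.
- Fatal febrile neutropenia lasting more than 5 days: covered.
- Febrile neutropenia fatal within 5 days and coded only as such: fails the duration condition. If graded 5, it also falls outside the catch-all.
- Fatal anaemia, or fatal marrow failure without bleeding: if graded 5, outside both general criteria. If the earlier Grade 4 phase is used instead, the myelosuppression criterion still requires more than 1 week, or more than 3 weeks after intervention, and death may come first.

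**Step 3: which grade decides.** The severity paragraph of Section 7.4.5 has the investigator record both the onset grade and the worst grade, and does not say which one settles DLT status. Section 7.4.2 and the outcome paragraph of Section 7.4.5 treat death as the outcome of an event. The wording therefore leaves open whether a fatal event that began at Grade 4 counts. For anaemia, thrombocytopenia and neutropenia this does not fully help: the first criterion already names them, so placing them under the catch-all strains the word *other*.

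**Step 4: what follows under Sections 3.1.1.1 and 8.2.** Suppose one such death occurs among the first three patients at a level and there is no other DLT.
- Counted: 1 DLT, so three more patients are added if the DMC recommends it.
- Not counted, patient retained: 0 DLTs, so the rule points to the next level.
- Not counted, and Section 8.2 read as requiring the full 5 weeks: the patient leaves the DLT Evaluable Analysis Set. Under Section 4.3.4 the DMC is consulted on replacement when a patient is discontinued for related adverse events.

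**Step 5: can the effect be sized?** With a per-patient DLT probability p, the chance of escalating past a level is (1−p)³ + 3p(1−p)⁵. The shift caused by the gap depends on how much of p consists of these deaths. The documents give no such rate, and do not reproduce the CTCAE terms that would show which haematological events can be graded 5. Any figure would also assume that the DMC did not intervene. No number follows from the documents.

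**The case against.** The strongest reply is that adjudication belongs to the rule itself: the sentence giving the DMC the final say stands in the same section as the escalation rule. A fatal event is a serious adverse event, reportable within 24 hours. The DMC reviews each level (Section 4.4), and under Section 5.3 "patients will be allocated to the highest dose level cleared by the DMC". The sponsor can halt dosing under Section 4.4.1. At Dose Level 1, any related event of Grade 3 or higher already brings in two more patients. *Grade 4* may also be shorthand for the severe end of the scale, since the infusion-reaction criterion uses it in the same way. All of this stands as evidence that the practical risk is low. It does not remove the defect, because the DMC decides whether an event qualifies against this same definition, and Section 4.4.1 rests on judgement and names no death.

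A reader might infer three stronger things that the documents do not support.
- *That related deaths in general escape the definition.* They do not; Step 2 shows that most are covered.
- *That the stagger within a level would be shortened without oversight.* Section 3.1.1.1 says "If no DLT is observed in the first patient, two subsequent patients will receive the treatment dose, but at least two days apart", against at least two weeks between the second and third patients when the first has a DLT. Section 4.4 adds that "the enrollment to the dose level will continue without the need of feedback from the DMC". That waiver applies only when the first patient has had no DLT in the first two weeks, and for a fatal event the DMC decides that question. The route would rarely be open.
- *That the gap raises the chance of escalation by a stated amount.* Step 5 shows why no such amount can be given.

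**Conclusion.** The concern holds as a minor defect in the wording of a decision threshold. On a literal reading, related fatal anaemia, related fatal marrow failure without bleeding, and febrile neutropenia fatal within 5 days and coded only as such meet no DLT criterion. A reading that includes some of them is available, but nothing in the text requires it. The conclusion rests on the wording alone, not on any assumed event rate. The affected set is narrow, and its size cannot be fixed from the documents. With DMC adjudication in place, it is unlikely that such a death would be ignored.

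**What to change.** Add one criterion to Section 3.1.1.2: *Any Grade 5 AE (fatal outcome) possibly or probably related to IMP*, with no duration condition. This settles both the grade and the duration questions. It also brings the patient into the DLT Evaluable Analysis Set, since Section 8.2 admits any patient who has a DLT in the evaluation period. Optionally, change the catch-all to *Any other Grade ≥4 hematological AE* so that the list is consistent. The cost is one line of protocol wording, plus a check that no completed dose level had such an event. No new data or patients are needed.

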#### **4.4.1. Trial Stopping Rules**

If any of the following occur, administration of the IMP will be stopped, and recruitment will be put on hold at least temporarily until DMC feedback is received to confirm if the trial can continue:

1. AEs or frequency of AEs that, in the judgment of the sponsor, are deemed to warrant immediate review by the DMC
2. Any other safety finding assessed as related to Lu-DTPA-omburtamab that, in the opinion of the DMC or sponsor, contraindicates further dosing of trial patients.

If any of these occur, an immediate cumulative review of safety data with focus on the AE in question will be conducted by the DMC to determine whether dosing and further recruitment should be resumed, the protocol modified, or whether the trial should be discontinued. Review and approval of the Sponsor Safety Committee and approval by the regulatory authorities is

required for resumption of the trial, should the trial be interrupted due to one of the above-mentioned safety findings.

Any patients who have received the IMP and are currently in the trial at the time trial stopping criteria are met will continue to be followed by the investigator for safety.

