#### Serious Adverse Events:

Serious AEs should be reported from signing the ICF until 5 weeks after the patient's last dose. Thereafter and during both the follow-up and post-trial monitoring periods, only SAEs considered related to IMP or related to the presence of the indwelling catheter system, or new onset of cancers regardless of causality, should be reported, until death or at least 10 years after end of trial, whichever comes first.

All events meeting the definition of an AE must be collected and reported in the eCRF. SAEs, DLTs (Part 1), and AESIs (whether serious or non-serious) should be reported both in the eCRF and on the clinical AE report form.

During each contact with the trial site staff, the patient must be asked about AEs, for example by asking: "Have you experienced any problems since the last contact?" All AEs observed by the

investigator or patient must be reported by the investigator and evaluated unless specifically excluded. All SAEs and AEs leading to discontinuation of IMP either observed by the investigator or patient must be reported by the investigator and evaluated.

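### A Part 1 Cycle 2 event meeting the DLT criteria need not be discussed by the DMC before its next preplanned meeting, and if it is non-serious it need not reach the DMC sooner

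*Combined protocol and SAP*

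**What the plan says.** **Cycle 1.** Section 3.1.1.2 defines DLTs as qualifying related events "occurring within 5 weeks after first IMP administration in Cycle 1 of Part 1". Section 3.1.1.1 bases escalation on DLTs "observed during Cycle 1 and the number of patients evaluable for DLTs".

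**Cycle 2.** If an event of the same kind occurs in Cycle 2 of Part 1, Section 3.1.1.2 says "these will be discussed at the first upcoming preplanned DMC meeting", and Section 4.4 repeats the rule. The Part 1 escalation meetings in Section 4.4 come "following completion of the first 5-week treatment cycle (Cycle 1) for the last patient in each dose level".

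**Faster routes to the DMC.**
- Section 3.1.1.1: "The DMC will receive all SAE on an ongoing basis". Section 4.4 repeats this duty, again naming SAEs.
- Section 4.4: "an unplanned DMC meeting can be held at the request of either the DMC or the Sponsor Safety Committee".
- Section 4.4.1: dosing stops and the DMC reviews if the sponsor judges that AEs warrant immediate review, or for a related safety finding that, "in the opinion of the DMC or sponsor, contraindicates further dosing of trial patients".
- Section 7.4.5.6: for significant safety issues the sponsor decides on immediate action, which includes prompt notice to the DMC.

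**Reporting to the sponsor.** Sections 3.1.1.2 and 7.4.5.1 require DLTs within 24 hours. Section 7.4.4 sets the same limit for AESIs, and the recipient is the sponsor. Section 7.4.5 adds: "SAEs, DLTs (Part 1), and AESIs (whether serious or non-serious) should be reported both in the eCRF" and on the clinical AE report form. Appendix 2 expects eCRF entry within 5 working days, shortened to 24 hours only for dosing and AEs in Part 1 Cycle 1.

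**The concern.** The Part 1 primary objective (Section 2.1.1) is the tolerability of up to two cycles, in a first-in-human trial in children. The meeting that releases the next dose level is tied to the last patient's Cycle 1, so some or all of Cycle 2 at that level is still to come. A related Cycle 2 event that would have counted as a DLT a few weeks earlier then has no mandatory DMC discussion until the next preplanned meeting. If it is non-serious, nothing plainly requires that the DMC be told of it before then.

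The affected child receives no further Part 1 dose, since two cycles is the maximum. Those who could benefit from earlier review are children at the same level still awaiting Cycle 2 and children being treated at the next, higher level. Myelosuppression is the expected toxicity: Section 1.2.1 reports cytopenia-related events in 81.7% and 87.5% of patients in the two 131I-omburtamab trials. Those figures cover cytopenia events in general, so they show that the type of event is plausible, not how often one would meet the DLT criteria in Cycle 2 and be judged non-serious.

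**Working it through.** There is no stated figure to reproduce. The check is a comparison of provisions followed by a calendar.

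**Which events must reach the DMC early?**
- Serious: yes. SAE transmission is mandatory and continuous (Sections 3.1.1.1 and 4.4).
- Non-serious AESI, for example a non-serious Grade 3 nervous system disorder: 24 hours to the sponsor (Section 7.4.4), but no provision plainly sends it on to the DMC.
- Non-serious and not an AESI, for example Grade 4 neutropenia lasting more than 1 week and judged non-serious: no provision plainly sends it to the DMC, and the sponsor deadline is unclear.

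**Why the sponsor deadline is unclear.** Read narrowly, a DLT is a Cycle 1 event (Section 3.1.1.2) and 24-hour eCRF entry is confined to Part 1 Cycle 1 (Appendix 2), so a Cycle 2 event is due within 5 working days. Read broadly, Section 7.4.5 tags DLTs to Part 1 without a cycle, Section 7.4.5.1 names DLTs without a cycle, and Section 8.5.1 uses the term for events outside the evaluation period, so 24 hours applies. Sites could reasonably differ.

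**Calendar inputs.** Dosimetry on Day 1 and treatment on Day 8 (Section 3.1.1); Cycle 2 dose 35 days after dosimetry (Appendix 3, Table 7, footnote 1); two weeks of observation after the first treatment dose, then two patients at least two days apart (Section 3.1.1.1). Assumed, because the protocol gives neither: the DMC meets L days after the last patient completes Cycle 1, and the next level starts on the meeting day.

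The stagger can be read two ways, for a three-patient level with L = 0:

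| | A: only treatment doses wait | B: dosimetry also waits |
|---|---|---|
| Dosimetry | Days 1, 15, 17 | Days 1, 22, 24 |
| Treatment | Days 8, 22, 24 | Days 8, 29, 31 |
| Cycle 2 dose | Days 36, 50, 52 | Days 36, 57, 59 |
| Level meeting | 17 + 35 = Day 52 | 24 + 35 = Day 59 |

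**First-patient event on the day of its Cycle 2 dose (Day 36).** Wait = meeting day − 36: 52 − 36 = 16 days (A), 59 − 36 = 23 days (B). The second patient's Cycle 2 dose (Day 50 or 57) falls before the meeting and the third's on the meeting day. For cytopenia that must last more than 1 week, the criterion is met only after Day 43 (36 + 7) even if onset is on the dosing day. The wait from then is under 9 days (52 − 43) or under 16 days (59 − 43), but the criterion can still be met before the second patient's dose.

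**Last-patient event after that meeting.** Count from this patient's Cycle 2 dose, which falls on the meeting day when L = 0. The next level's treatment doses fall at 7, 21 and 23 days (A) or 7, 28 and 30 days (B); its meeting is at 51 or 58 days. For an event on days 1 to 35, the wait is 51 − 35 = 16 to 51 − 1 = 50 days (A), or 58 − 35 = 23 to 58 − 1 = 57 days (B). Overall: 16 to 57 days. That meeting comes 28 days after the higher level's last treatment dose (51 − 23 or 58 − 30).

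**Sensitivity, L = 14.** The first-patient wait becomes 30 to 37 days (16 + 14, 23 + 14). The higher level's meeting moves to 51 + 28 = 79 or 58 + 28 = 86 days, so an event on days 15 to 35 waits 44 to 64 days (79 − 35, 79 − 15) or 51 to 71 days (86 − 35, 86 − 15). A later meeting covers more of Cycle 2 but lengthens the wait for what it misses.

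**The case against.** The strongest reply is that the plan already has adequate routes. SAE sharing is compulsory, and Section 7.4.2 counts medically important events as serious, so much prolonged Grade 4 cytopenia could qualify. Even on the narrow reading the sponsor should see the event in the eCRF within 5 working days and can then use Section 4.4, 4.4.1 or 7.4.5.6. At the next level, one child is treated and observed for two weeks before the others. Sections 3.1.2, 3.2 and 4.4 bring toxicity from both cycles into the RP2D and the number of Part 2 cycles. Sections 7.4.5.3 and 7.4.5.5 group DLTs with SAEs, which could be read as bringing them under SAE sharing. Finally, DMC workflow is left to the charter.

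Much of this stands. The affected class is narrow, its frequency cannot be estimated from the documents, and the charter or Figure 2 may already settle the matter. What remains is that, for a non-serious event, every visible route to earlier DMC review depends on someone's judgement, and the grouping of DLTs with SAEs does not settle whether a Cycle 2 event is a DLT at all. The two-week observation helps, but with no DLT in the first child, Section 4.4 lets enrolment at that level continue without DMC feedback. The RP2D review comes too late for children dosed during escalation.

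A reader might go further and infer that the preplanned meeting is the DMC's first required contact with any Cycle 2 DLT-type event. The documents do not support that: for serious events, earlier transmission is mandatory, and only the discussion can wait.

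**Conclusion.** The point holds in a limited form. For related Part 1 Cycle 2 events meeting the Section 3.1.1.2 criteria, the only mandatory DMC discussion is at the next preplanned meeting. Serious events must reach the DMC earlier; non-serious ones, AESIs included, need not. For those that are not AESIs, 24-hour reporting to the sponsor is ambiguous.

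With minimum stagger, a three-patient level and no meeting or recruitment lag, the waits are 16 to 23 days for a first-patient event on its Cycle 2 dosing day and 16 to 57 days for a last-patient event after the level's meeting. These are waits for mandatory discussion, not for sponsor awareness. They apply to Dose Levels 2 to 5; at a level expanded to six, the gap mainly concerns the added patients.

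A reader might also take the share of Cycle 2 follow-up falling after the meeting as the size of the gap. At no lag, 16 + 2 + 0 = 18 of 105 patient-days precede the meeting under A and 23 + 2 + 0 = 25 under B, leaving 83% and 76% after it. Those shares do not measure the gap, because they include time in which serious events reach the DMC through SAE sharing, and they move with the assumed lag. Nor does the point question restricting DLTs and the 3+3 count to Cycle 1. It is a low-cost safety improvement, between optional and recommended.

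**What to change.** In Sections 3.1.1.2, 4.4 and 7.4.5.1, state that any related Part 1 Cycle 2 event meeting the Section 3.1.1.2 criteria, serious or not, is reported to the sponsor within 24 hours and forwarded promptly to the existing DMC for written or ad hoc review, without waiting for the preplanned meeting. Align the charter, or cite it if it already says this. Keep the Cycle 1 DLT window and the 3+3 count as they are, and leave any hold to DMC and sponsor judgement under Sections 4.4 and 4.4.1.

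The cost is protocol and charter wording, an occasional extra review by a committee that already exists, and possibly slightly slower escalation.
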